Main Analyses: First, we will fit a series of negative binomial regression implemented in the SAS® GENMOD procedure with each fracture outcome as the dependent variable; duration of follow-up as an offset to account for each participant's exposure; treatment arm as the main independent factor of interest; and any covariates deemed important as additional independent variables in sensitivity analyses. The incident rate ratio and its statistical significance at $\alpha=0.05$ level for the primary outcome of all new fractures will serve as a formal test of the main fracture reduction hypothesis (H1). Second, we will fit a series of linear mixed models using the SAS® MIXED procedure with raw and percent change each from baseline in each of the continuous outcomes representing laboratory measures related to safety as the dependent variable; treatment arm, follow-up time point (12-/24-/36-month, as available) and their interaction as the

fixed effects of interest; and a subject random effect. For some measures, we will fit simpler models (due to only one planned post-infusion assessment) using the GLM procedure with raw and percent change each as the dependent variable, and treatment arm as the main factor of interest. We will appropriately construct sets of contrasts to test various hypotheses of interest by comparing the said change over time between the two arms. Third, we will fit a series of logistic regression models using the SAS® LOGISTIC procedure with each incident dichotomous adverse event during the 36-month follow-up (any and specific types of adverse events) as the dependent variable, and treatment arm as the independent factor of interest. The resulting odds ratios and levels of significances will be used to test the specific hypotheses for Aim 2. We will repeat all main analysis after stratification by institutional setting (assisted living/nursing home).

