Findings from the proposed trial will be most useful if (a) we can also identify a target sub-population of the long-term care that is most likely to benefit from zoledronic acid and/or least likely to experience side effects; and (b) we can speculate whether fracture reduction or non-reduction in women, despite improvement in BMD, depends on bone microstructure as measured by TBS. Therefore, using several techniques, some with an exploratory data mining philosophy, we will identify such sub-populations to address Aim 3(a). First, we will include all baseline clinical and laboratory characteristics, one-at-a-time, as an additional fixed effect in the models above, along with an interaction term with treatment group. Statistical significance of the interaction term will be interpreted as a patient baseline characteristic whose levels exhibit potentially differential treatment effects and/or safety profiles. Second, we will stratify analyses by such baseline criteria to actually obtain preliminary estimates of subgroup-specific treatment effects/safety differences. Third (data mining), using only the active arm, we will fit a series of logistic regression models using the SAS® LOGISTIC procedure and classification tree models using Salford Predictive Miner® software (Salford Systems, Inc., San Diego, California) with incident fracture as the dichotomous response variable; and baseline characteristics as predictors. Logistic models are more efficient when associations are linear, and hard-to-discover higher order interactions and non-linearity and/or multicollinearities among predictors do not exist, while classification tree models are more efficient when they do exist. Thus we will use both methods to obtain areas under the receiver operator characteristic curve (AUROCC) to quantify predictive accuracy, and use the results from the method with a greater AUROCC. For logistic regression we will use the backward elimination and for classification trees minimum misclassification-complexity cost tree to guard against overfitting. We will use the method of DeLong to obtain statistical significance of the differences in predictive accuracy between the models. For predicting improvements in continuous BMD change outcomes, we will employ a similar approach but with standard multiple linear regression and regression tree models and proportion of explained variance (R²) to quantify predictive accuracy.

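### The active-arm data-mining step for Aim 3(a) models fracture risk on treatment, without follow-up time, and cannot show who benefits from zoledronic acid

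*Protocol*

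**What the plan says.** The protocol (Statistical Considerations, text on Aim 3(a)) wants to "identify a target sub-population of the long-term care that is most likely to benefit from zoledronic acid" and lists three techniques for this.

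- **First:** baseline characteristics enter the main models "one-at-a-time, as an additional fixed effect in the models above, along with an interaction term with treatment group".
- **Second:** analyses are stratified by the characteristics so found, to give "preliminary estimates of subgroup-specific treatment effects/safety differences".
- **Third:** "Third (data mining), using only the active arm, we will fit a series of logistic regression models", together with classification trees, "with incident fracture as the dichotomous response variable; and baseline characteristics as predictors". Both methods are fitted, and the plan is to "use the results from the method with a greater AUROCC". The stated protections are backward elimination for the logistic model and, for the tree, a "minimum misclassification-complexity cost tree to guard against overfitting".

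The main fracture model, described under Main Analyses, uses "duration of follow-up as an offset to account for each participant's exposure". The primary outcome section expects incomplete follow-up from women who die, withdraw or move before three years. The SAP document carries only the overview paragraph, so the detail on Aim 3(a) is in the protocol.

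**The concern.** The first two techniques compare arms, and the first inherits the follow-up offset for fractures. The third does neither. A model of fracture among treated women estimates their risk while on the drug. It contains nothing about what would have happened to the same women without it.

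The yes/no response adds a second problem. A woman who dies early without a fracture counts the same as one observed fracture-free for three years, so a characteristic linked to early loss can look protective.

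The first technique takes characteristics singly and the second follows from it. The third is therefore the only step that clearly builds a profile from several characteristics. A published multi-characteristic target group would thus come from a prognostic model. The protocol gives no rule for turning predicted fracture risk into benefit, in either direction.

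**Working it through.** The documents give no figure for this technique, so there is nothing to reproduce. The check is an illustration.

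**Inputs from the protocol.** Control rate 0.11 per year (Scientific Background, nonvertebral fractures in long-term care). Rate ratio for prior hip or vertebral fracture 2–3 (same section; 2.5 in the worked example). Treatment rate ratio 0.65 (Study Design & Methods, 35% reduction in clinical fractures).

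**Assumptions not in the documents.** 40% with prior fracture, 15% loss per year, 150–250 women per arm, gamma frailty variance 0–1.

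**1. Identifiability.** Control rate without prior fracture: 0.11 / (0.6 + 0.4 × 2.5) = 0.0688 per year. With prior fracture: 2.5 × 0.06875 = 0.1719. Active rates at 0.65 times these: 0.0447 and 0.1117. Three-year risk is 1 − exp(−3 × rate):

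- active arm: 28.5% with prior fracture, 12.5% without, odds ratio 2.8;
- control arm: 40.3% and 18.6%.

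Now hold the active rates fixed and vary only the control rates, which the third technique never uses:

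| Control rate, prior / no prior | Absolute reduction, prior / no prior (points) |
|---|---|
| 0.1719 / 0.0688 | 11.8 / 6.1 |
| 0.1719 / 0.0447 | 11.8 / 0 |
| 0.1117 / 0.0688 | 0 / 6.1 |
| 0.1117 / 0.0447 | 0 / 0 |

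All four rows produce the same active-arm data, at any sample size.

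**2. A true difference in effect.** Take rate ratios 0.45 with prior fracture and 0.90 without. Active rates are 0.1719 × 0.45 = 0.0773 and 0.0688 × 0.90 = 0.0619, giving risks of 20.7% and 16.9%. The absolute reductions are 40.3 − 20.7 = 19.6 points and 18.6 − 16.9 = 1.7 points. The active-arm odds ratio is only 1.28. In simulation (4,000 trials per setting) the active-arm logistic model flags the factor at the 5% level in 7–10% of trials. A two-arm rate-ratio interaction test using follow-up time flags it in 34–40% at 250 per arm and 23–27% at 150.

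**3. No difference in relative effect.** With rate ratio 0.65 in everyone, the active-arm model flags prior fracture in 46–90% of trials at 250 per arm (30–71% at 150), over prior-fracture rate ratios 2–3 and frailty variance 0–1. If the drug does nothing, it flags prior fracture in about 55–97% (37–85%). The interaction test flags it in about 4–6% in both cases. The first percentages are power to detect a risk factor and the last is a type I error rate. The point is that the active-arm model responds in much the same way whether or not the drug works.

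**4. Follow-up time.** At the active rate 0.11 × 0.65 = 0.0715, the chance of any fracture is 1 − exp(−0.0715) = 6.9% after one year and 1 − exp(−0.2145) = 19.3% after three, a 2.8-fold difference from observation time alone. Next, suppose a factor changes only mortality. With death hazard h, P(fracture observed) = 0.0715/(0.0715 + h) × [1 − exp(−3(0.0715 + h))]. For annual mortality of 10%, 20%, 30% and 40% this gives 16.6%, 14.2%, 12.1% and 10.1%. The odds ratios against 10% are 0.83, 0.69 and 0.56. With 250 women and 40% prevalence, the factor is flagged in about 7% of trials at 20% mortality and about 15–29% at 30–40%, against 4–5% in a rate model with an offset.

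**5. Choice by AUROCC.** Backward logistic selection on 20 pure-noise predictors (assumed number; stay level 0.05 assumed) gives a mean apparent AUROCC of 0.59–0.60 at n = 250 and 0.62 at n = 150, where the truth is 0.50. No tree figure is given, because it depends on cost settings that the documents do not state.

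**The case against.** The step is labelled exploratory, the subgroup estimates are called preliminary, and the primary hypothesis is untouched. The first two techniques already compare arms, and the control rates missing from the third are observed in the trial. All of this is true. It limits the damage, but it does not make the third technique estimate what the aim asks for.

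The strongest argument is that benefit may be meant on the absolute scale. Under a constant rate ratio, higher-risk women do gain more: 11.8 against 6.1 points in the first row of the table. On-treatment risk then ranks women by absolute benefit. This stands, but only under a constant rate ratio. That is the very assumption Aim 3(a) sets out to examine, and one arm cannot test it.

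The follow-up point is weaker. It matters only if baseline characteristics relate to death or dropout. The larger distortions need 30–40% annual mortality in one group, and the documents give no mortality rate for enrolled women, who must be ambulatory. At 10% against 20% the effect is small.

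The AUROCC point is secondary. Pruning and backward elimination are planned; what is missing is a stated hold-out or cross-validation for the comparison that picks the method. Finally, the second technique might stratify by several criteria jointly. The text does not say, so the third being the only multi-characteristic step is a reading of the plan.

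**Conclusion.** The concern holds for the third technique only. As written, it is the wrong analysis for its stated purpose: it gives prognosis on treatment and cannot by itself identify who benefits. The identifiability failure does not depend on any assumed rate or sample size. The illustrated sizes do: with true rate ratios of 0.45 and 0.90, the active-arm model detects the factor in 7–10% of trials, against 23–40% for the two-arm interaction. Those figures rest on the assumed prevalence, loss, frailty and arm size. The distortion from unequal follow-up is real in direction but uncertain in size. The consequence is confined to what Aim 3(a) can conclude. The plan should be changed, but the primary analysis is not at risk.

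**What to change.** Refit the third technique on both arms, with treatment and treatment-by-predictor terms and log follow-up time as an offset. Interaction trees or model-based partitioning of the negative binomial model are two options. Report between-arm differences for each sub-population on the absolute as well as the relative scale, because a rate-ratio interaction alone does not show who gains most in absolute terms. Choose between methods on cross-validated performance.

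If the active-arm model is kept, account for follow-up time, label it prognosis on treatment, and state that it will not be used to name a sub-population that benefits. The parallel approach for BMD change, if also confined to treated women, needs the same label or a control comparison.

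The cost is SAP wording and modest programming on the same data. The downside is limited power for interactions (23–40% in the example above), so fewer sub-populations will be declared.

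### Aim 3(a) chooses between logistic and tree models, and quantifies their accuracy, by an AUROCC for which no cross-validation or optimism correction is specified

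*Protocol*

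**What the plan says.** The plan for this step is in the Protocol, Statistical Considerations, in the paragraph on Aim 3(a). It is the third of three techniques and is restricted to treated women: "Third (data mining), using only the active arm". Logistic regression and classification trees are fitted "with incident fracture as the dichotomous response variable; and baseline characteristics as predictors".

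Both methods are used to obtain "areas under the receiver operator characteristic curve (AUROCC) to quantify predictive accuracy", and the analyst will then "use the results from the method with a greater AUROCC". Two safeguards follow: backward elimination for the logistic model and, for the tree, the "minimum misclassification-complexity cost tree to guard against overfitting". The comparison ends with a test: "We will use the method of DeLong to obtain statistical significance of the differences in predictive accuracy between the models". For change in BMD the protocol will "employ a similar approach but with standard multiple linear regression and regression tree models and proportion of explained variance" (R-squared).

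The protocol does not say on which data the AUROCC or R-squared is computed. It mentions no hold-out sample, cross-validation, bootstrap correction or external validation for either. The SAP repeats only the overview paragraph of the protocol's statistical section and adds nothing on Aim 3(a).

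**The concern.** One number does two jobs here: it picks the method, and it is the accuracy attached to the result. An AUROCC computed on the women who were used to select and fit the model is too high, because selection and fitting exploit chance patterns in those women. The amount differs between a stepwise logistic model and a tree, so the two figures are not on a common footing. Taking the larger adds a further upward push.

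The named safeguards act on the size of the model. A pruned tree still takes its node fracture proportions from the women who defined the nodes, and a reduced logistic model keeps the predictors that happened to look strong. Even if the tree software prunes by internal cross-validation, that picks a tree size by misclassification cost. It does not yield an out-of-sample AUROCC for either method.

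The DeLong test treats the two sets of predicted scores as fixed. Applied to same-sample fits, it makes no allowance for variable selection or tree growing on the same women.

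At stake is the credibility of a profile of women who do or do not fracture on zoledronic acid, in a section whose purpose is to find the residents most likely to benefit.

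**Working it through.** **No figure to reproduce.** The documents give no sample size, predictor count or AUROCC for this step. The check is therefore a simulation of the rule, reading the AUROCC as same-sample.

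**Inputs from the protocol.** Active arm only; fracture yes/no; backward-elimination logistic against a cost-complexity-pruned tree; the larger AUROCC wins. The Scientific Background gives 11% per year for nonvertebral fracture. Over three years that is 1 − 0.89³ = 0.295, or 1 − exp(−0.33) = 0.281. With the 35% reduction in clinical fractures cited under Study Design & Methods, 0.295 × 0.65 = 0.19. These figures serve only to place the assumed fracture proportion at 20–30%.

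**Assumptions.** Active arm of 75, 150 or 300; 10, 20 or 40 independent normal predictors; p ≤ 0.05 to stay in the logistic model; tree pruned by 5-fold cross-validated cost, minimum leaf 5. The truth was either no signal or three linear predictors (log-odds 0.45, 0.45 and 0.35 per SD). True AUROCC was measured in 4,000 new subjects. There were 60–100 replicates per scenario, so a percentage has a standard error of at most √(0.25/60) = 6.5 points.

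**Equal class priors, minimum-cost tree, 20 predictors, 25% with fracture.** Inflation = apparent − true AUROCC of the chosen model.

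| Truth | n | Apparent | True | Inflation |
|---|---|---|---|---|
| No signal | 75 | 0.81 | 0.50 | 0.31 |
| No signal | 150 | 0.81 | 0.50 | 0.31 |
| No signal | 300 | 0.79 | 0.50 | 0.29 |
| Linear | 75 | 0.85 | 0.54 | 0.31 |
| Linear | 150 | 0.82 | 0.57 | 0.25 |
| Linear | 300 | 0.81 | 0.58 | 0.23 |

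Under the linear truth the rule took the model with the lower true AUROCC in 54%, 65% and 76% of replicates at n = 75, 150 and 300.

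**Number of predictors (n = 150, no signal).** With 10 predictors: 0.827 − 0.500 = 0.327. With 40: 0.828 − 0.501 = 0.327.

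**Other readings of the pruning rule (n = 150, 20 predictors, 25% with fracture).**

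| Tree | Truth | Apparent | True | Inflation | Tree chosen |
|---|---|---|---|---|---|
| Equal priors, 1-SE | No signal | 0.641 | 0.500 | 0.141 | 23% |
| Data priors, minimum cost | No signal | 0.649 | 0.497 | 0.152 | 23% |
| Equal priors, 1-SE | Linear | 0.727 | 0.578 | 0.149 | 30% |
| Data priors, minimum cost | Linear | 0.740 | 0.581 | 0.159 | 25% |

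With equal priors and the minimum-cost tree, the tree was chosen in 52–85% of replicates. The preferred method therefore reverses with the settings, while the inflation stays positive. Its range over all scenarios is 0.141 to 0.327.

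**Choosing by 5-fold cross-validated AUROCC instead**, with elimination and pruning repeated in each fold (equal priors, minimum-cost tree, 20 predictors, 25% with fracture):

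| Truth | n | Reported | True | Difference |
|---|---|---|---|---|
| No signal | 150 | 0.513 | 0.499 | 0.014 |
| No signal | 300 | 0.506 | 0.500 | 0.006 |
| Linear | 150 | 0.618 | 0.592 | 0.026 |
| Linear | 300 | 0.658 | 0.639 | 0.019 |

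Under the linear truth the tree is on average the worse model (true AUROCC 0.542 against 0.609 at n = 150, and 0.548 against 0.644 at n = 300). In the same replicates its selection fell from 73% to 22% at n = 150 and from 68% to 5% at n = 300.

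The R-squared comparison for BMD was not simulated.

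**The case against.** The best defence is that the protocol is silent, not wrong. A reader might infer that it plans a same-sample AUROCC, but it never says so, and an analyst could cross-validate without departing from the text. That stands: the supportable statement is that no out-of-sample evaluation is specified, and the inflation is conditional on the same-sample reading. The silence still matters, because a rule that both selects and reports has to name its data, and the protocol lists its protections against overfitting without including this one.

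Three stronger readings are tempting and are not supported:

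- *The rule systematically favours the tree, or the more overfit method.* Class priors, leaf size and pruning rule are not given, and under two plausible choices the tree is picked in only 23–30% of replicates.
- *The reported accuracy would be fictitious.* That holds only if no predictor carries signal. Under the linear truth the chosen model's true AUROCC was above 0.50, so part of the reported accuracy was genuine.
- *The trial's conclusions are at risk.* The protocol describes its approach as "using several techniques, some with an exploratory data mining philosophy". The other two Aim 3(a) techniques (interaction terms and stratified estimates) do not use the AUROCC, and the negative binomial test of the primary outcome is untouched.

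It is also fair to say that the protocol does address overfitting. Its safeguards help with model size but leave the AUROCC uncorrected.

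**Conclusion.** The point holds as a gap in an exploratory analysis that is worth closing. The protocol chooses a method and quantifies its accuracy by AUROCC without specifying cross-validation, a hold-out or optimism correction, and its named safeguards do not supply one. If the AUROCC is same-sample, the chosen model's accuracy is overstated in every scenario examined. The size depends on assumed arm size, fracture proportion, predictors and pruning, none of which the documents give for this step. About 0.15 is typical of the stricter pruning settings, and 0.2 to 0.33 of the equal-prior minimum-cost tree. No direction of preference between the methods can be claimed. The weakness of the DeLong test and of the R-squared comparison follows by reasoning only; neither was quantified. Consequences are confined to the Aim 3(a) prediction and subgroup statements.

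**What to change.** In the Aim 3(a) paragraph, and in the SAP, which is silent on this step:

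- State that the choice between methods and the reported accuracy use repeated 10-fold cross-validated or bootstrap optimism-corrected AUROCC, and the corresponding R-squared for BMD change.
- Require the whole of backward elimination and of tree growing and pruning to be repeated inside each fold or resample.
- Compare the methods on out-of-fold predictions with a bootstrap confidence interval. If DeLong is kept, apply it only to those predictions.
- Report apparent and corrected values side by side.
- Name the candidate predictors, the significance level to stay, the class priors and costs, the minimum leaf size and the pruning rule, since these decide which method wins.

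Taking the larger of two cross-validated figures still left about 0.01 to 0.03 of optimism in the simulation. Placing the choice of method inside an outer resampling loop would address that.

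The cost is a little more programming and lower reported AUROCC and R-squared. No new data are needed and the primary analysis does not change.

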Post-hoc pivotal trial subgroup analyses comparing those >75 to those <75 years suggest zoledronic acid (17), teriparatide (18) and denosumab (19) are efficacious in older very healthy women who qualify for a clinical trial. These trials only included women who were healthy, cognitively intact, fully ambulatory, and able to sign their own consent. Fracture reduction data in frail elderly are lacking.

Osteoporosis Therapy in Frail Elderly may not be Clinically Effective:

There are little data on frail elderly or non-healthy LTC residents (20,21). In addition, the limited available data questions the efficacy of bisphosphonate in frail elderly. For example, in the HIP study, fracture reduction was not demonstrated with an oral bisphosphonate in women over age 80 enrolled based on clinical risk factors only (22). Furthermore, the PI's ZEST study in frail LTC residents, demonstrated improvement of BMD at the hip and spine with zoledronic acid, however no fracture reduction trend was observed. The majority of these patients were cognitively impaired, sedentary and had multiple comorbid conditions, excluding them from an industry trial. Fracture reduction data are lacking in these vulnerable patients. The March 2011 NIH/ASBMR Forum on Aging and Skeletal Health echoed the critical need for osteoporosis research, a fracture reduction study and treatment for frail LTC residents (23).

Why would therapy fail in frail elderly? Both skeletal and nonskeletal factors in frail elderly may mask a fracture reduction benefit from a potent bisphosphonate. Despite the improvement in bone density and reduction in bone turnover (both independent contributors to fracture reduction), frail individuals may not benefit due to severely compromised skeletal integrity from poor trabecular connectivity (disconnected rods and plates), increased trabecular fragments,

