For Aim 3(b), the association between zoledronic acid, BMD, TBS and fracture reduction will be explored in two ways. First, we proposed above to examine the effect of the study drug on TBS with standard linear models. Second, using only the active arm of the trial, we will fit a negative binomial model with number of fractures within 3 years as the dependent variable; and baseline BMD, 3-year change in BMD, baseline TBS, and 3-year change in TBS as independent variables. The statistical significance of regression coefficients for TBS measures will be interpreted as evidence supporting that fractures over a 3-year period depend on TBS and its changes over the same period independent of BMD.

Exploratory Analyses: We will perform exploratory analyses to assess the robustness of results and make more refined conclusions. For example, we will stratify adverse event and fracture

analyses to identify any differences between short- and long-term effects and/or within organ systems.

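### Aim 3(b) asks whether fracture reduction depends on TBS, but its only fracture model uses treated women alone and cannot separate prognosis from effect modification

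*Protocol*

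**What the plan says.** In the Protocol's Statistical Considerations, the paragraph that introduces Aim 3 sets the question as "whether fracture reduction or non-reduction in women, despite improvement in BMD, depends on bone microstructure as measured by TBS". The Scientific Background gives the motive: "frail individuals may not benefit due to severely compromised skeletal integrity from poor trabecular connectivity".

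The Aim 3(b) paragraph lists two analyses. For the first, "we proposed above to examine the effect of the study drug on TBS with standard linear models"; this compares the arms, but the outcome is TBS. The second is the only one with a fracture outcome: "using only the active arm of the trial, we will fit a negative binomial model with number of fractures within 3 years" as the response, and "baseline BMD, 3-year change in BMD, baseline TBS, and 3-year change in TBS as independent variables". Significant TBS coefficients "will be interpreted as evidence supporting that fractures over a 3-year period depend on TBS and its changes" "over the same period independent of BMD".

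Under Aim 3(a), the Protocol also plans to enter "all baseline clinical and laboratory characteristics, one-at-a-time, as an additional fixed effect in the models above, along with an interaction term" with treatment group. It names no particular characteristic. The SAP repeats only the statistical overview and says nothing about Aim 3.

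**The concern.** Fracture reduction is a contrast between arms. Asking whether it depends on TBS is asking whether the drug's rate ratio changes with TBS, which is effect modification. The Background's conjecture, that the drug may fail where trabecular structure is poor, has the same form. Neither listed analysis estimates that quantity: one has no fracture outcome and the other has no comparison arm.

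At stake is the mechanistic conclusion. If the trial shows no fracture reduction, Aim 3(b) is where a reader will look to see whether poor microstructure explains it. A TBS coefficient from treated women can be fully explained by low TBS being a risk factor for fracture, with the drug working equally well at every TBS level.

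**Working it through.** **Plan's own figures.** The documents give no sample size, dispersion, loss rate or TBS effect for this aim, so there is no figure to reproduce. The core point is algebraic; the simulation only illustrates it.

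**Step 1: what the active arm identifies.** Let x be the number of SDs below mean TBS.

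- Control: log rate = a + b·x
- Treated: log rate = a + d + (b + g)·x
- Drug rate ratio at x: exp(d + g·x)

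Here exp(b) is prognosis and exp(g) is effect modification. The aim concerns g. The active-arm model estimates b + g.

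- Truth A (prognosis 1.5 per SD lower TBS, no modification): b + g = ln 1.5 + 0 = 0.405. The rate ratio is 0.65 at every TBS level.
- Truth B (no prognosis, modification 1.5): b + g = 0 + ln 1.5 = 0.405. The rate ratio is 0.65 × 1.5 = 0.98 at 1 SD below the mean, 0.65 at the mean, and 0.65 / 1.5 = 0.43 at 1 SD above.

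Treated women's fracture data have the same distribution under A and B, so more patients cannot help. If b = 0.4 and g = −0.4, the slope is zero although modification is real.

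**Step 2: simulation inputs.** From the Protocol: nonvertebral rate 0.11 per year (Scientific Background) and drug rate ratio 1 − 0.35 = 0.65 (Study Design & Methods, clinical fractures). Assumed: vertebral rate 0.08 per year, so the control rate is 0.11 + 0.08 = 0.19; dispersion 0.7; loss 15% per year; BMD-TBS correlation 0.3; 100, 150 or 250 per arm; two-sided 5% Wald tests; 1,000 replicates per cell. The active-arm model has the four planned terms, in treated women reaching 3 years (0.85³ = 61%, about 61, 92 or 154 women). The two-arm model has treatment, BMD, TBS, treatment × TBS and treatment × BMD, with a log follow-up offset, in all randomized women.

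**Step 3: percent of trials significant, at 100/150/250 per arm.**

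| Truth (ratio per SD lower TBS) | Active-arm baseline TBS | Two-arm treatment × TBS |
|---|---|---|
| Prognosis 1.5 only (A) | 39/51/70 | 6/6/5 |
| Modification 1.5 only (B) | 38/54/73 | 31/44/59 |
| Prognosis 1.3 only | 18/24/39 | 5/6/4 |
| Modification 1.3 only | 18/26/39 | 15/21/32 |
| Both 1.3 | 56/74/92 | 17/22/33 |

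A repeat run at 150/250 per arm gave 48/73% (A) and 49/68% (B) for the active-arm model, against 3/6% and 44/60% for the interaction. With dispersion 0.3-1.5 and annual loss 10-20% (150 per arm, ratio 1.5), the active-arm model was significant in 42-61% under A; the interaction was significant in 6-7% under A and 35-47% under B.

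**Step 4: the null case.** A simpler model (TBS only, rate 0.11 per year, dispersion 0.5, 200 per arm) with a zero slope in treated women but a log-rate slope of −0.4 per SD of TBS in controls gave a significant active-arm coefficient in 4.5% of trials. The two-arm interaction was significant in 47%.

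**Step 5: precision of the interaction.** The 95% limits lie a factor of about 1.75/1.57/1.42 either side of the estimate. As a check at 150 per arm: SE = ln 1.57 / 1.96 = 0.230. For a ratio of 1.5, power ≈ Φ(0.405/0.230 − 1.96) = Φ(−0.20) = 0.42. For 1.3, Φ(0.262/0.230 − 1.96) = Φ(−0.82) = 0.21. The simulated values are 44% and 21%.

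**Step 6: the Aim 3(a) screen, if it includes TBS.** Treatment, TBS and treatment × TBS without BMD was significant in 5/8/4% under A and 34/46/63% under B at 100/150/250 per arm. When BMD alone modifies the drug effect, the screen flags TBS falsely in 8/8/11% (BMD ratio 1.5 per SD). At a BMD ratio of 2.0 it does so in 20/29% at 150/250 per arm, against 4/4% with treatment × BMD in the model.

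**The case against.** The strongest reply is that the two-arm test is already planned. The Aim 3(a) screen covers all baseline characteristics, and its silence on TBS means little because it names none. Step 6 shows that it would separate truths A and B about as well as the model proposed here. Much of this stands, and a reader who inferred that the plan has no two-arm look at TBS would go too far. What remains is that the text does not confirm that TBS is included, does not link the screen to Aim 3(b), and does not adjust for BMD, whereas Aim 3(b) wants a reading independent of BMD. The gain from treatment × BMD is small unless BMD modification is strong.

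Second, the stated interpretation is only that fractures depend on TBS, not that drug benefit does, and the aim is exploratory. That is correct: the fault is a mismatch between question and model, not an explicit false claim. But the paragraph offers this model as its way of exploring fracture reduction, so its coefficients will be read as the answer.

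Third, a reader might infer from truths A and B that a significant coefficient is equally likely whether or not the drug effect varies with TBS. That holds only when the treated-arm slopes match. With prognosis fixed at 1.3, the active-arm model is significant in 18/24/39% without modification and 56/74/92% with it. Zero prognosis is a limiting case; the Protocol's TBS section reports that TBS predicts fracture independently of BMD. That report also means a significant coefficient is to be expected with no modification at all.

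A reader might also infer that fractures themselves distort TBS change and so bias its coefficient badly. No section says that a fracture shifts TBS. With an assumed shift of 0.3-0.8 SD per lumbar fracture, false positives were 6-14%, against 5-6% with none. The documents support only the narrower point that TBS change is measured over the same period as the fractures and needs a month-36 scan.

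**Conclusion.** The concern holds in limited form. The only Aim 3(b) model with a fracture outcome cannot apportion its TBS coefficient between prognosis and effect modification. A significant coefficient shows association among treated women. A null coefficient is no answer either: prognosis and modification can cancel, although with low TBS raising risk this requires modification opposite to the Background's conjecture, and at the sizes simulated a null is often just low power.

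This non-identifiability rests on no assumed number. The percentages do: they depend on assumed sample size, dispersion, loss and TBS effects, and should be read for direction. The aim is exploratory, and the primary fracture test is unaffected. What changes is whether the trial may say that poor microstructure explains a lack of fracture reduction.

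**What to change.** For Aim 3(b), name one two-arm negative binomial model in the form of the Main Analyses, with a log follow-up offset, in all randomized women with a baseline TBS. Its terms are treatment, baseline BMD, baseline TBS, treatment × baseline TBS and treatment × baseline BMD. Base any statement about fracture reduction on the treatment × TBS estimate and its confidence interval.

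Keep the active-arm model as descriptive. Report its TBS and TBS-change coefficients as associations among treated women with month-36 scans, and replace *depend on* with *are associated with*. Adding the control arm would not make the TBS-change coefficient causal, because change is measured after randomization.

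The cost is some wording and one extra exploratory model. Baseline TBS in both arms is already needed for the planned analysis of the drug's effect on TBS, so no new data are required. The drawback is low power: about 15-32% for an interaction ratio of 1.3 per SD and 31-59% for 1.5, at an assumed 100-250 per arm. The plan should say in advance that a null interaction is inconclusive.
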